### 17.2.3 Special Adverse Events Categories

Special safety summaries will be performed for special adverse event categories (SPAEC):

- Acne-like rash
- Skin reaction
- Infusion related reaction
- Neurotoxicity associated AEs
- Mucositis
- Septic events
- Cardiac events

The latest special AE list provided by drug safety will also be referred. If there are any difference, the special AE list provided by drug safety has higher priority.

The SPAEC “Infusion related reaction” is further divided into the following medical concepts:

- Allergy/anaphylaxis
- Dyspnea
- Fever
- Other

The SPAEC “Cardiac events” is further divided into the following medical concepts:

- Congestive Heart Failure
- Arrest
- Infarction-ischemia
- Arrhythmia
- Sudden death

The AEs are associated to a category by matching with a list of predefined PT.

The AEs are associated to a category by matching with a list of predefined PT. For the Infusion related reactions, there are 2 categories of events:

- AEs flagged in the definition as “Inclusion of AEs on Day 1 only” = No: any TEAE with the corresponding preferred term will be taken into account
- AEs flagged in the definition as “Inclusion of AEs on Day 1 only” = Yes: AEs with the corresponding preferred term occurred at Cycle 1 Day 1

A listing with all preferred terms for each category and medical concept will be provided.

The following summaries will be produced for all SPAEC:

- Number of subjects with SPAEC events, overall and by medical concept if applicable
- Number of subjects with SPAEC events by NCI-CTCAE grade (any, 1, 2, 3, 4, 5,  $\geq 3$ ), overall and by medical concept

Special summaries will be prepared separately for events on “skin reactions” and “acne-like rash” (=SPAEC1) only for the patients who received at least one dose of cetuximab as follows:

- Time until first occurrence of any “SPAEC1”
  - 1-7 days,
  - 8-14 days,
  - 15 -21 days,
  - 22-28 days,
  - 29-35 days,
  - 36-42 days,
  - $\geq 43$  days
- Time until first occurrence of grade 3/4 “SPAEC1” by category:
  - 1-7 days,
  - 8-14 days,
  - 15 -21 days,
  - 22-28 days,
  - 29-35 days,
  - 36-42 days,
  - $\geq 43$  days
- The resolution status of SPAEC1 after cetuximab discontinuation
  - 0 days (resolved during treatment),
  - resolution within days 1-30,
  - 31-60,
  - 61-90,

- 91-120,
- >120.
- The resolution status of SPAEC1 Grade 3/4 after cetuximab discontinuation
  - 0 days (resolved during treatment),
  - resolution within days 1-30,
  - 31-60,
  - 61-90,
  - 91-120,
  - >120.

The time until first occurrence of any “SPAEC1” (in days) will be calculated as

(first onset date of any “SPAEC1” related event with any grade – first dosing day of cetuximab +1).

The time until first occurrence of grade  $\geq 3$  “SPAEC1” will be calculated similarly. These statistics will be categorized for those subjects with any grade  $\geq 3$ .

The resolution status of SPAEC1 will be prepared for all subjects in the cetuximab treatment arm with SPAEC1. The resolution status will be presented by calculating the duration (in days) of SPAEC1 after last cetuximab infusion as follows:

Duration = resolution date of SPAEC1 – last dosing date of cetuximab +1

For subjects with overlapping events the last resolution date will be taken. Duration of SPAEC1 per subject (any, grade  $\geq 3$ ) will be categorized into intervals of 30 days length up to a sensible limit (e.g., 120 days), >sensible limit, at least one episode ongoing (including outcome death), unknown. Unknown is defined as at least one episode of resolved with SPAEC1 unknown resolution date, but without any further ongoing SPAEC1. Events with a resolution date before the last cetuximab infusion will be assigned a value of 0 days, which represents the subjects with resolution during cetuximab treatment.

Subjects with missing onset or resolution dates of “SPAEC” and subjects with “SPAEC” ongoing at the final visit will be flagged in the individual subject data listings indicating the type of missing variable.

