### Data handling after cut-off date:

Data after cut-off do not undergo the cleaning process. The only exception is the date of death on “Death” eCRF page.

Generally, data obtained after the cut-off will not be displayed in any listings or used for summary statistics, e.g., laboratory values of samples taken after data cut-off, AE with onset date after data cutoff, etc. will not be included in any analysis or listing.

The cut-off will be implemented at SDTM level.

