### 12.1 Disposition of Subjects and Discontinuations

Descriptive statistics will be used to summarize subject disposition and reason for discontinuation, based on the electronic case report form (eCRF) data.

The following information will be reported:

- Number of subjects screened.
- Number of subjects who discontinued from the study prior to randomization, overall and grouped by reason (i.e. Subject did not meet all eligibility criteria, Withdrew informed consent, Progressive disease, Adverse event, Lost to follow-up, Death, Other as reported on the “Study Entry” eCRF page).
- Number of randomized subjects in each treatment arm
- Number of randomized subjects who received no treatment in each treatment arm
- Number of randomized subjects ongoing on treatment in each treatment arm (subject initiated one or more treatment as reported on the “Cetuximab Administration”, “Cisplatin Administration”, “Carboplatin Administration” and “5-FU Administration” eCRF page and at least one of initiated treatments is not discontinued as reported on the “Cetuximab Termination”, “Cisplatin Termination”, “Carboplatin Termination” and “5-FU Termination” eCRF pages)
- Number of randomized subjects who are off treatment in each treatment arm and reason for treatment discontinuation. To be accounted as off all treatments a subject must discontinue all the initiated treatments (as reported on the “Cetuximab Termination”, “Cisplatin Termination”, “Carboplatin Termination” and “5-FU Termination” eCRF pages). If the treatments are discontinued for different reasons, the reason for discontinuation of the last treatment will be taken into account.
- Number of randomized subjects who discontinued the treatment after randomization, grouped by treatment arm and main reason separately for each treatment component (as reported on the “Cetuximab Termination”, “Cisplatin Termination”, “Carboplatin Termination” and “5-FU Termination” eCRF pages). For cisplatin, the number of randomized subjects who definitely discontinue cisplatin and number of those who switched to carboplatin will also be displayed.
- Number of randomized subjects who stopped assessments grouped by treatment arm and main reason (as reported on “End of Assessment Visit” eCRF page)

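### The skin-reaction resolution table is labelled as after cetuximab discontinuation, but it also takes in subjects still on cetuximab at the cut-off and mixes them into its ongoing row

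*SAP*

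**What the plan says.** SAP 17.2.3 (Special Adverse Events Categories) defines SPAEC1 as skin reactions and acne-like rash. It plans special summaries "only for the patients who received at least one dose of cetuximab". One of them is titled "The resolution status of SPAEC1 after cetuximab discontinuation", with bands of 0 days, 1-30, 31-60, 61-90, 91-120 and more than 120 days. A second table does the same for severe reactions.

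The computing rules follow in the same section:

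- Population: "The resolution status of SPAEC1 will be prepared for all subjects in the cetuximab treatment arm with SPAEC1".
- Time: "Duration = resolution date of SPAEC1 – last dosing date of cetuximab +1".
- Resolved on treatment: "Events with a resolution date before the last cetuximab infusion will be assigned a value of 0 days".
- Not resolved: the text adds rows for "at least one episode ongoing (including outcome death), unknown". The bullet list of bands does not show these rows.

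Two other parts of the SAP bear on this. Section 11 sets the data cut: "Generally, data obtained after the cut-off will not be displayed in any listings or used for summary statistics". Section 12.1 expects subjects to be on treatment at that point, because it plans the "Number of randomized subjects ongoing on treatment in each treatment arm".

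Protocol 7.1.7 has the outcome and resolution date of skin reactions collected every 3 months after the end-of-efficacy-assessment visit, until death or the end of the trial.

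**The concern.** The title describes what happens once the drug is stopped. The population and the time origin do not require stopping. For a subject on weekly cetuximab at the cut-off, the last dosing date is only the last infusion before the data were cut. An open rash in that subject is correctly called ongoing, but it says nothing about resolution after discontinuation.

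The ongoing row therefore merges three states: still on cetuximab, stopped and unresolved, and dead. A reader cannot separate them. There is also no rule on minimum follow-up or censoring, so a subject who stopped shortly before the cut-off has no chance of reaching the later bands.

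At stake is the readability of one descriptive table. It bears directly on the background statement in Protocol 3.7.4 that skin reactions generally resolve after treatment ends. Protocol 7.1.7 collects data that serve it.

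**Working it through.** The plan gives no figure for this table, so there is nothing to reproduce. The check traces the rules and then illustrates the size.

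**Rule trace (SAP 17.2.3 and 11)**

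| Subject at the cut-off | Where the rules put the subject |
|---|---|
| Stopped; resolved before last infusion | 0 days |
| Stopped; resolved 29 days after last infusion | 29 + 1 = 30, band 1-30 |
| Stopped; resolved 30 days after | 30 + 1 = 31, band 31-60 |
| Stopped; resolved 120 days after | 120 + 1 = 121, band >120 |
| Stopped; unresolved | ongoing |
| Died with open reaction | ongoing |
| **Still on drug; open reaction** | **ongoing** |
| **Still on drug; resolved before last infusion** | **0 days** |
| **Still on drug; resolved 3 days after last infusion, before the cut** | **3 + 1 = 4, band 1-30** |

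None of the last three rows describes resolution after discontinuation. A subject whose last infusion was 20 days before the cut-off can reach at most 20 + 1 = 21, so every band after 1-30 is closed.

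**Size at the PFS cut-off (illustration)**

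Inputs from the documents:
- about 240 subjects randomized 2:1, so 160 and 80 (Protocol 5.1);
- cut-off at 144 PFS events, expected at about 22 months (Synopsis);
- EXTREME PFS medians of 5.6 and 3.3 months (Protocol 3.7.2);
- recruitment over about 24 months (Protocol 5.1).

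Assumptions: exponential PFS, uniform accrual over R = 18 to 24 months, Arm B median 3.3 to 4.3 months, and cetuximab given until progression.

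If the cut-off t falls before accrual ends, follow-up is uniform on 0 to t. The share of enrolled Arm A subjects still event-free is then (1 − e^(−λt)) / (λt).

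For R = 24, t = 20.95 months gives 144 events:
- Enrolled: 160 × 20.95/24 = 139.7 in Arm A and 69.8 in Arm B.
- Arm A: λ = ln 2/5.6 = 0.1238, λt = 2.593, event-free (1 − 0.0748)/2.593 = 35.7%, so 139.7 × 0.643 = 89.9 events.
- Arm B: λ = ln 2/3.3 = 0.2100, λt = 4.400, event-free 22.4%, so 69.8 × 0.776 = 54.2 events.
- Total: 89.9 + 54.2 = 144, at about 21 months, close to the stated 22.

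For R = 18, t = 17.08: λt = 2.114 and (1 − 0.1208)/2.114 = 41.6% of 151.8, or 63 subjects. With an Arm B median of 4.3 months the shares are 35.1% (R = 24) and 40.8% (R = 18).

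If a fraction p stops cetuximab before progression, the hazard of stopping becomes λ/(1 − p). For R = 24 and Arm B median 3.3:
- p = 0.2: (1 − 0.0391)/3.241 = 29.6%, about 41 subjects.
- p = 0.4: (1 − 0.0133)/4.322 = 22.8%, about 32 subjects. It is 22.4% with an Arm B median of 4.3.

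Stopped within 120 days (d = 120/30.4375 = 3.94 months) of the cut-off, R = 24, treated to progression: [3.94 + (1 − 0.1218)/0.1238 − (1 − 0.0748)/0.1238]/20.95 = 17%, about 24 subjects. For R = 18 it is 19%.

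Protocol 3.7.4 says more than 80% may develop skin reactions. At 80%, the 32 to 63 subjects still on drug include about 0.8 × 32 = 26 to 0.8 × 63 = 50 who have had one. Those with a reaction still open are a subset. The documents do not give its size.

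With the E5397 medians (4.2 and 2.7 months, Protocol 3.7.2) and R = 24, the event-free share is 30%.

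**Size at the OS cut-off**

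Add the EXTREME OS medians of 10.1 and 7.4 months and the rule of 180 deaths or 12 months after the last randomization. For R = 24, the 180th death falls at about 32.1 months, so follow-up runs from 8.1 to 32.1 months. The share still on drug is (e^(−0.1238 × 8.1) − e^(−0.1238 × 32.1))/(0.1238 × 24) = (0.367 − 0.019)/2.97 ≈ 12%. It is about 11% for R = 18, and 3 to 8% with 20 to 40% early stopping.

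**The case against.** The strongest reply is that this is a labelling matter in a descriptive, single-treatment safety table. Several parts of that reply stand.

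- A reader might infer that the late bands lack follow-up altogether, since general adverse event reporting ends at the Safety Follow-up visit. The documents do not support that. Protocol 7.1.7 makes an exception for skin reactions, and Table 1.1 marks adverse event assessment at survival follow-up. The bands can be observed; the cut-off only truncates them for recent stoppers.
- A reader might infer that every subject still on cetuximab counts as unresolved. They do not. Those whose reaction resolved before the last infusion go to 0 days, and only open reactions go to the ongoing row, which is separate from the time bands.
- A reader might infer that the table understates resolution. The net direction is not shown. Subjects still on drug enter the 0 days row as well as the ongoing row, and the share with an open reaction is unknown.
- SAP 5 says results go into the trial report and into an addendum using data to the OS cut-off. If this table is repeated there, fewer subjects are affected. The SAP does not say that it will be.
- Subjects on treatment are counted by arm (SAP 12.1), and reactions ongoing at the final visit are flagged in listings.

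What the reply does not remove is the conflict between the title and the population. The disposition count cannot be linked to the ongoing row, and a listing flag does not correct a summary table.

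**Conclusion.** The point holds in a limited form. Under the stated rules, subjects still on cetuximab with an open reaction are reported in the same row as subjects unresolved after stopping, under a title that covers only the latter. Recent stoppers have not yet had time to reach the later bands, and the table does not show this.

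At the PFS cut-off, about 35 to 42% of enrolled Arm A subjects could still be on cetuximab if treated to progression. With 24-month accrual and 20 to 40% early stopping, the share is about 22 to 30%. A further 17 to 19% (treated to progression) would have stopped within the preceding 120 days. These are illustrations that rest on exponential PFS, EXTREME-like medians and uniform accrual. They size the group at risk of being mislabelled; the number actually affected is smaller, because the reaction must be unresolved. At the OS cut-off the share still on drug falls to about 12% or less.

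The primary endpoint and the comparison between arms are not affected. The correction is worth making because it is nearly free.

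**What to change.** In SAP 17.2.3, for both the any-grade and the severe-grade table:

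1. Base the post-discontinuation rows and their denominator on subjects with a recorded Cetuximab Termination before the cut-off. SAP 12.1 already uses that eCRF page.
2. Show subjects still on cetuximab at the cut-off on a separate line, divided into open and resolved reactions.
3. Keep the 0 days row.
4. Split deaths from the other ongoing cases.
5. For the ongoing row, summarize the time from the last infusion to the last skin follow-up or the cut-off, so that short follow-up is visible.
6. List the ongoing and unknown rows with the bands, so that the bullets match the text, and say whether the table is repeated at the OS cut-off.

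A time-to-resolution estimate is optional. If one is added, the SAP must say how deaths are handled.

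The cost is a wording change and one or two extra table rows. No new data are needed.

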### 17.2.4 3 Tier Approach

The Crude Rate is calculated as number of subjects with specific AE divided by the total number of subjects at risk expressed as percentage.

The Exposure Adjusted Incidence Rate (EAIR) is defined as the number of subjects with a specific AE divided by the total exposure-time among the subjects in the treatment group at risk of the initial occurrence of the event. If a subject has multiple events, the exposure period of the first

event is used. For a subject with no event, the exposure period is censored at the last follow-up time for the AE summarization period. EAIR will be measured in 1000 subjects within 1 year.

The AEs identified for Tier 1 reporting in this trial are:

- Infusion related reactions
- Skin reactions
- Hypomagnesaemia.

The first two categories are composite and will be based on the list of preferred terms based on the latest MedDRA version and provided by Merck Drug Safety. Hypomagnesaemia includes one preferred term “Hypomagnesaemia”.

All the other AEs will be further classified into Tier 2 or Tier 3 based on the Rule-of-4 and Crude Rate threshold. If there are 4 or more subjects with the reported term in any treatment group and Crude Rate is equal or superior to 5%, that term will be included in Tier 2. Otherwise, it will be included in Tier 3.

For the Tier 1 the following summaries will be presented:

- Number of subjects and percentage by category in each treatment group accompanied by Crude Rate difference between treatment groups with 95% CI. CI will be generated using Miettinen & Nurminen (MN) method.
- Forest tree showing Crude Rate and Crude Rate difference with 95% MN CI
- Number of subjects, number of subject-years and EAIR with 95% CI using Poisson method by category in each treatment group. In addition, EAIR difference between treatment groups along with 95% CI will be shown.

For the Tier 2 following summaries will be presented:

- Number of subjects and percentage by SOC and PT and overall in each treatment group accompanied by Crude Rate difference between treatment groups with 95% CI. CI will be generated using MN method.
- Number of subjects, number of subject-years and EAIR with 95% CI using Poisson method by SOC and PT in each treatment group. In addition, EAIR difference between treatment groups along with 95% CI will be shown.

For the Tier 3 following summaries will be presented:

- Number of subjects and percentage by SOC and PT and in each treatment group accompanied by Crude Rate difference between treatment groups.

- Number of subjects, number of subject-years and EAIR by SOC and PT in each treatment group. In addition, EAIR difference between treatment groups will be shown.

No multiplicity adjustment will be applied for Tier 1 and 2 AEs.

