Planned trial period (first subject in-last subject out)	The third quarter of 2015-The fourth quarter of 2018
Trial Registry	This trial was registered on clinicaltrials.gov as well as chinadrugtrials.org.cn

Objectives:

Primary objective: The primary objective of this trial is to evaluate whether progression-free survival (PFS) time, as assessed by an Independent Review Committee (IRC), in subjects receiving cetuximab in combination with cisplatin plus 5-fluorouracil (5-FU) is longer than that in subjects receiving cisplatin plus 5-FU alone in the first-line treatment of recurrent and/or metastatic squamous cell carcinoma of the head and neck (SCCHN).

Secondary objectives: The secondary objectives are to compare the 2 treatment arms in the following:

- PFS time, as assessed by the Investigator
- Overall survival (OS) time

- Best overall response (BOR) rate
- Disease control rate (DCR)
- Duration of response
- Safety

Methodology:

This is an open-label, randomized, parallel-group trial. At the end of a 28-day screening period, all eligible subjects will be randomly assigned into treatment Arm A or B in a 2:1 ratio. Subjects in Arm A will receive a maximum of 6 cycles of chemotherapy (cisplatin plus 5-FU) and cetuximab weekly in the absence of progressive disease (PD), as assessed by the Investigator, and unacceptable toxicity. After 6 cycles of treatment, subjects who derive clinical benefit will continue treatment with cetuximab as monotherapy until either PD or unacceptable toxicity. Subjects in Arm B will receive the same chemotherapy regimen as Arm A alone for a maximum of 6 cycles in the absence of PD and unacceptable toxicity.

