Note: The expected frequencies in brackets are defined as: very common (\geq 1/10), common (\geq 1/100, < 1/10), uncommon (\geq 1/1,000, < 1/100), rare (\geq 1/10,000, < 1/1,000), very rare (< 1/10,000), frequency not known (cannot be estimated from the available data).

Skin reactions: Skin reactions may develop in more than 80% of subjects and mainly present as acne-like rash and/or, less frequently, as pruritus, dry skin, desquamation, hypertrichosis, or nail disorders (e.g., paronychia). Approximately 15% of the skin reactions are severe, including single cases of skin necrosis. The majority of skin reactions develop within the first 3 weeks of treatment. They generally resolve without sequelae over time following cessation of treatment, if the recommended adjustments in dose regimen are followed. According to the National Cancer Institute – Common Terminology Criteria for Adverse Events (CTCAE) version 4.03, Grade 2 skin reactions are characterized by rash affecting up to 50% of body surface area (BSA), while Grade 3 reactions affect equal or more than 50% of BSA. Skin lesions induced by cetuximab may predispose subjects to superinfections (e.g., with Staphylococcus aureus), which may lead to subsequent complications, e.g., cellulitis, erysipelas or potentially fatal outcomes such as staphylococcal scalded skin syndrome or sepsis.

Infusion-related reactions: Mild or moderate infusion-related reactions are very common and comprise symptoms such as fever, chills, dizziness, or dyspnea that occur in a close temporal relationship, mainly to the first cetuximab infusion. Severe infusion-related reactions may occur commonly, but the outcome is rarely fatal. They usually develop during or within 1 hour of the initial cetuximab infusion, but may occur after several hours or with subsequent infusions. Although the underlying mechanism has not been identified, some of these reactions may be anaphylactoid/anaphylactic in nature and may include symptoms such as bronchospasm, urticaria, decrease or increase in blood pressure, loss of consciousness or shock. In rare cases, angina pectoris, myocardial infarction or cardiac arrest have been observed.

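### The exposure-adjusted rate for Tier 1 infusion related reactions includes time in which Day 1-only terms cannot be counted, which biases its arm comparison toward Arm A

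*SAP*

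**What the plan says.** SAP 17.2.4 names three Tier 1 categories: infusion related reactions, skin reactions and hypomagnesaemia. Each gets a crude rate per arm, the crude-rate difference with an MN 95% CI, and a forest plot ("Forest tree showing Crude Rate and Crude Rate difference with 95% MN CI"). Each also gets an EAIR per arm, shown with the number of subject-years, and an EAIR difference with 95% CI.

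The EAIR is the number of subjects with the event "divided by the total exposure-time among the subjects in the treatment group at risk of the initial occurrence of the event". Subjects with an event contribute time up to their first event. For all others: "For a subject with no event, the exposure period is censored at the last follow-up time for the AE summarization period". No separate risk window is set for any category.

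SAP 17.2.3 splits the infusion-reaction terms in two. For unflagged terms, "any TEAE with the corresponding preferred term will be taken into account". Flagged terms are limited to "AEs with the corresponding preferred term occurred at Cycle 1 Day 1". On the Tier 1 lists, 17.2.4 says only this: "The first two categories are composite and will be based on the list of preferred terms", supplied by drug safety. It does not mention the Day 1 flag.

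Treatment length differs by design. Protocol 5.1 continues cetuximab in Arm A until progression or unacceptable toxicity. For the control arm the Synopsis says: "Subjects in Arm B will receive the same chemotherapy regimen as Arm A alone for a maximum of 6 cycles". SAP 17.1 closes the treatment-emergent window 30 days after the last dose.

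**The concern.** An incidence rate compares arms fairly when each unit of person-time is time in which the event could have been counted. For a term counted only at Cycle 1 Day 1, that holds for one day. After it, an event-free subject adds months to the denominator and can add nothing to the numerator. This also sits badly with the at-risk wording in the SAP's own EAIR definition.

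Unflagged terms are likely to be front-loaded as well. Protocol 3.7.4 places these reactions close in time "mainly to the first cetuximab infusion".

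Because Arm A is treated for longer, the surplus time dilutes its rate more than Arm B's, so the direction of the bias is known in advance. At stake is how one of three pre-selected cetuximab risks is read: two Tier 1 comparisons of the same event could disagree, and the SAP does not say which to rely on.

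**Working it through.** **No plan figure to reproduce.** The available text gives no EAIR, no mean exposure and no infusion-reaction rate by arm. Risks and exposures below are assumptions, shown over a range.

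**Inputs**
- 240 subjects randomised 2:1, so 160 v 80 (Protocol Synopsis).
- Proxy for treatment time: the EXTREME PFS medians, 5.6 v 3.3 months (Protocol 3.7.2).
- Arm B cap: 6 x 21 = 126 days = 4.14 months. Tail: 30 days = 0.99 month.
- All events placed on Day 1, the case that the flag describes.

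**Formula.** With Day 1 risk p and mean AE period T in years,

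EAIR = 1000 x p / [p x (1/365.25) + (1 - p) x T].

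**Mean AE period, months**
- (a) Medians plus tail: 5.6 + 0.99 = 6.59 v 3.3 + 0.99 = 4.29. Ratio 1.54.
- (b) Exponential means, Arm A capped at 12 months, Arm B at 18 weeks, plus tail. A: (5.6/ln 2)(1 - exp(-12 ln 2/5.6)) + 0.99 = 7.24. B: (3.3/ln 2)(1 - exp(-4.14 ln 2/3.3)) + 0.99 = 3.75. Ratio 1.93.
- (c) As (b) with Arm A uncapped: 5.6/ln 2 + 0.99 = 9.06 v 3.75. Ratio 2.42.

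Example, (a) with p = 10%: A = 100/(0.0003 + 0.9 x 6.59/12) = 202; B = 100/(0.0003 + 0.9 x 4.29/12) = 311.

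**Results (EAIR per 1000 subject-years, A v B; Wald-type Poisson 95% CI for the difference)**

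| Day 1 risk, A v B | (a) | (b) | (c) |
|---|---|---|---|
| 10% v 10% | 202 v 311, ratio 0.65 | 184 v 355, ratio 0.52 | 147 v 355, ratio 0.41 |
| 20% v 10% | 455 v 311, +144 (-123 to 411), ratio 1.46 | 414 v 355, +59 (-226 to 344), ratio 1.17 | 331 v 355, -24 (-296 to 247), ratio 0.93 |
| 30% v 5% | +632 (368 to 895) | +541 (281 to 801) | +398 (168 to 628) |

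With equal exposure of 5 months in both arms, 20% v 10% gives 599 v 266: +333 (55 to 610), ratio 2.25.

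**Break-even.** Ignoring the one-day term, the two EAIRs are equal when T_A/T_B = [pA/(1 - pA)]/[pB/(1 - pB)]. That is 2.11 for 10% v 5%, 2.25 for 20% v 10% and 2.43 for 30% v 15%.

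**Crude comparison for Day 1 terms.** Exposure does not enter. 20% v 10% (32/160 v 8/80) gives +10.0 points, MN 95% CI 0.0 to 18.7. Equal 10% risks give 0 (-9.3 to 7.5).

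**With later, unflagged events.** Add a common hazard of 0.02 per month after Day 1 (assumed) to equal 10% Day 1 risks. The EAIR ratio is then 0.81 in (a) and 0.72 in (b): the bias is smaller but still present. The crude rates become 21.1% v 17.4% in (a) and 22.1% v 16.5% in (b), so the crude difference now leans against Arm A because Arm A is observed for longer.

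**The case against.** The strongest reply is that nothing is concealed. The crude rate, its difference and its CI come first in the Tier 1 list, the forest plot shows only the crude results, and the subject-years printed with the EAIR make unequal exposure visible. This stands. A reader might infer that the plan can hide a doubled infusion-reaction risk; the SAP does not support that, since only the EAIR line is affected.

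A reader might also infer that the EAIR difference mainly measures treatment length. That is too strong. A 30% v 5% contrast stays clearly positive in every scenario, and a doubled risk vanishes only at exposure ratios of about 2.1 to 2.4, reached here only with uncapped Arm A treatment. The main analysis is expected about 22 months after trial initiation (SAP 8). Adding that cut-off to (c), with uniform accrual assumed over the 22 months, gives about 5.9 v 3.4 months, ratio 1.75. A 20% v 10% risk then gives about 505 v 394, with no reversal.

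Three further objections have weight. The documents give no Arm B infusion-reaction rate, so equal or doubled risks are illustrations. Only flagged terms are strictly Day 1; which terms those are depends on a list outside the documents, and carrying the flag into 17.2.4 is an inference from the shared category and the drug-safety list. For unflagged terms, later time is genuine time at risk, so dropping the EAIR for everything would lose a useful adjustment.

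What survives is that, for flagged terms, the stated rule gives a rate whose arm comparison is biased in a known direction.

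**Conclusion.** The concern holds in a limited form. Where the Day 1 flag applies, the EAIR and EAIR difference for infusion related reactions favour Arm A because of their denominator. Equal Day 1 risk makes Arm A look safer in all three scenarios (EAIR ratio 0.41 to 0.65). A doubled risk of 20% v 10% shrinks to a ratio of 0.93 to 1.46, against 2.25 with equal exposure, and its CI includes zero in each unequal-exposure scenario.

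These sizes rest on assumed risks, on PFS medians as a stand-in for treatment time, and on all events falling on Day 1. The direction rests only on the design and the counting rule. Unflagged terms in the composite would dilute the bias.

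Severity is minor. Protocol 8.5.4 plans no formal safety comparisons, no success criterion uses this line, and the crude comparison for Day 1 terms is sound and already planned.

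**What to change.** In SAP 17.2.4:
- State that the Day 1 flag of 17.2.3 applies to the Tier 1 infusion-reaction category.
- For flagged terms, limit the time at risk to Cycle 1 Day 1, or omit the EAIR and EAIR difference.
- Name the crude-rate difference with MN CI as the Tier 1 comparison for infusion related reactions.
- Keep the EAIR, if wanted, only for unflagged terms, which can occur throughout exposure.

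The cost is a line or two of SAP text and one EAIR row dropped or split. No new data are needed. If the row is split, the composite no longer has a single exposure-adjusted figure. The crude difference for unflagged terms still depends on length of observation, which is the reason to keep their EAIR beside it.
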